3 OBJECTIVES AND ENDPOINTS

In this pilot project, there are two objectives. Firstly, we will evaluate, in an open trial, whether iTEST is acceptable, indexed by adherence, and engages IA as a target, indexed by improved IA on trained

tasks and transfer on an untrained task in a different domain. Secondly, we will evaluate optimal dosing of the intervention, by whether go/no-go criterion for improvement is achieved at 8, 12, or 16 weeks.

Our go/no go criteria are threefold: 1) To demonstrate feasibility, the average adherence must be equal to or exceed 75%, 2) To show target engagement, we require a significant improvement in IA ($d > .50$) on both trained tasks, and 3) To show transfer of training, we require significant improvement in IA ($d > .50$) on the untrained Wisconsin Card Sorting Task. Criteria may be met prior to 16 weeks, at weeks 8 or 12 (Note: all participants continue through 16 weeks).

OBJECTIVES	ENDPOINTS	JUSTIFICATION FOR ENDPOINTS
Primary		
To evaluate the acceptability and preliminary impact on our target, IA	
Adherence defined as the ratio of completed mobile prompts completed divided by the number possible – 75% is the criterion
 
Clinically significant (Cohen's $d > 0.5$) improvement in trained introspective accuracy as measured by IA on our Verbal Learning and Memory Test and Mobile Electronic Test of Emotion Recognition tasks. These are administered 6x per week for 16 weeks.
 
Clinically significant (Cohen's $d > 0.5$) improvement in untrained introspective accuracy (global resolution score) on the WCST. The WCST is administered at baseline, 8, 12 and 16 weeks.
	
Adherence at a level of 75% is generally accepted in mobile intervention studies such as this
 
The reason that trained tasks are part of our Go/No Go criteria is because lack of improvement on trained tasks would call into question the ability of iTEST to modify IA, and would indicate need for program revisions. IA is calculated as the discrepancy (absolute) between each trial's correct performance from that estimated by the participant, which is nested within sessions and weeks.
 
An additional Go/No Go component is transfer of training to an untrained task-based measure of IA, the Meta-Cognitive Wisconsin Card Sorting Test¹³. IA on this task is also associated with functioning and improvement on this task would support that iTEST

OBJECTIVES	ENDPOINTS	JUSTIFICATION FOR ENDPOINTS
		leads to generalized improvement in IA.
Secondary		

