9.2 SAMPLE SIZE DETERMINATION

We used the Monte Carlo simulation capabilities of Mplus version 8.4⁵² to perform our power analyses. To determine our levels of power to detect changes in IA for the list-learning task or emotion recognition tasks equivalent to $d = |0.50|$ for R61 Aim 1, we specified three-level models with 1000 replications each wherein trials ($t = 18$) were nested within weeks ($w = 8, 12, \text{ or } 16$) that were further nested within persons ($n = 60$ or 48 in the case of 20% attrition). These models were similar to Figure 1 with the exception that changes in IB and IA at Level 3 were not regressed on intervention condition. As can be seen in Table 1, our power levels were excellent (i.e., $> .90$) across all combinations of sample size and week size, ranging from .91 for detecting changes in IA of $d = -0.50$ at 8 weeks with 48 participants to .97 for detecting changes in IA of $d = 0.50$ at 16 weeks with 60 participants.

To determine our levels of power to detect transfer-of-training for R61 Aim 1 and optimal dosing for Aim 2, we again specified three-level models with 1000 replications each wherein trials ($t = 18$) were nested within weeks ($w = 8, 12, \text{ or } 16$) that were further nested within persons ($n = 60$ or 48 in the case of 20% attrition). However, we modified these models such that they included an additional Truth and Bias model for the WCST transfer of training target at Level 2 that had a change in IB of $d = -0.50$ across the weeks. To reflect the fact that this in-laboratory tasks would only be measured at 0, 4, 8, 12, and 16 weeks, we specified that these measurements should have 62.5% missing data in the simulations (e.g., only completing 3 out of 8 weeks). As can be seen in Table 2, we should have more-or-less adequate levels of power to detect a change in IB for the in-lab assessment at 16 weeks with 48 participants (power = .77) and adequate power to detect a change in IB for the in-lab assessment at 12 and 16 weeks with 60 participants (power = .78 and .83, respectively).

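### The WCST transfer power in Section 9.2 was simulated for a different visit schedule and a different parameter from those in the go/no-go criterion; the direction of the error is unknown

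*Combined protocol and SAP*

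**What the plan says.** **Section 9.2** adds a WCST component to the three-level simulation that "had a change in IB of $d = -0.50$ across the weeks". On timing, it says that the in-laboratory "tasks would only be measured at 0, 4, 8, 12, and 16 weeks, we specified that these measurements should have 62.5% missing data", and explains the percentage by the example "only completing 3 out of 8 weeks". From this it reports power of .77 at 16 weeks with 48 participants, described as more or less adequate, and "adequate power to detect a change in IB for the in-lab assessment at 12 and 16 weeks with 60 participants", with values of .78 and .83. All three figures are given for IB.

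**Section 3** says "The WCST is administered at baseline, 8, 12 and 16 weeks". The Schedule of Activities (Section 1.3) agrees: the metacognitive WCST is marked at baseline and at days 56, 84 and 112.

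**The criterion.** Section 3 sets the transfer criterion as improvement in IA on the WCST with d above .50, and its endpoint table scores this as global resolution. Table 3 in Section 8.2 uses the same score. Section 8.1 describes the primary WCST measure as a difference between accuracy judgments and correctness. Section 9.4.1 defines IA as a regression slope and IB as a mean-level difference, then says that transfer will be judged on change in bias, accuracy or both.

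**The concern.** Section 9.2 offers these figures as support for 60 participants on the transfer criterion. That support holds only if the simulated data resemble the data to be collected and the simulated effect is the one on which the decision rests. Neither condition is met as written.

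All three go criteria must be satisfied, and under Section 4.1 the earliest assessment point that satisfies them sets the duration carried into the randomized phase. A reader who takes the figures at face value would believe that the chance of detecting transfer at weeks 12 and 16 is known and sufficient. In fact it has not been stated for the planned visits, and the text gives none for the named quantity.

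**Working it through.** **1. The plan's missing share.** Its convention is observed visits divided by weeks in the window. The assumed schedule has three visits by week 8 (0, 4, 8), so 1 − 3/8 = 62.5%. This reproduces.

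**2. The same convention in each window.**

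| Window | Assumed visits (0, 4, 8, 12, 16) | Missing | Planned visits (0, 8, 12, 16) | Missing |
|---|---|---|---|---|
| 8 weeks | 3 of 8 | 62.5% | 2 of 8 | 75% |
| 12 weeks | 4 of 12 | 66.7% | 3 of 12 | 75% |
| 16 weeks | 5 of 16 | 68.75% | 4 of 16 | 75% |

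The quoted powers are for 12 and 16 weeks, where 62.5% does not match even the assumed schedule. Applied there it implies .375 × 12 = 4.5 and .375 × 16 = 6 WCST occasions, against 3 and 4 planned.

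**3. Can the stated powers be reproduced?** No. The variance components, alpha and missing-data mechanism are not in the text. Two rough checks, assuming two-sided alpha of .05:

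- Simple pre-post change in baseline SD units: power = Φ(0.5√n / √(2(1 − r)) − 1.96). As the correlation r runs from 0 to .7, this gives .69 to .99 for n=48 and .78 to 1.00 for n=60. No single r matches all three figures, because weeks 12 and 16 differ at the same n.
- Scaling .77 from n=48 to n=60: the noncentrality is 1.96 + 0.74 = 2.70; 2.70 × √(60/48) = 3.02; Φ(3.02 − 1.96) = .855, against .83 stated. With 1,000 replications the Monte Carlo SE is about √(.8 × .2/1000) = .013 per figure, so this gap is unremarkable.

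**4. Which way does the schedule error go?** For a linear change over weeks, the information from one person depends on the sum of squared deviations of the visit weeks (Sxx). For k weeks drawn at random from w consecutive weeks, the expected value is (k − 1) × w(w + 1)/12. Random placement is an assumption, since Section 9.2 does not state it.

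| Window | Simulated, random weeks | Planned, fixed weeks |
|---|---|---|
| 8 weeks | 2 × 8 × 9/12 = 12 | (0, 8): 32 |
| 12 weeks | 3.5 × 12 × 13/12 = 45.5 | (0, 8, 12): 74.7 |
| 16 weeks | 5 × 16 × 17/12 = 113.3 | (0, 8, 12, 16): 140 |

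On this measure the planned schedule carries more information in every window, despite fewer visits.

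**5. Illustration with between-person variation in change.** This is a simplified random-slope model for a mean-level (IB-type) change, with assumed within-person correlation .3 to .7, calibrated to .83 at 16 weeks with n=60 and 62.5% missing at random.

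| Case | Stated | Model, 62.5% random | Model, 75% random | Model, fixed at planned weeks |
|---|---|---|---|---|
| n=60, week 16 | .83 | .83 (calibrated) | .67–.73 | .86–.87 |
| n=48, week 16 | .77 | .74–.75 | .58–.63 | .78–.79 |
| n=60, week 12 | .78 | .74–.77 | .57–.64 | .85–.86 |

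The answer changes direction with how the missing weeks are represented. Simply replacing 62.5% by 75% in the existing simulation would not settle the matter; the visits have to be placed at their actual weeks.

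**6. The parameter.** Steps 4 and 5 concern IB only. Under Section 9.4.1 the WCST contributes one judgment and one performance value per visit, so IA as a slope would rest on at most four pairs per person by week 16 and two by week 8. Power for that quantity cannot be derived from the documents or from the IB figures.

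**The case against.** **IB is a planned quantity.** Section 9.4.1 allows transfer to be judged on IB, and the measure described in Section 8.1 reads more like a mean-level difference than a slope. This stands: IB is not foreign to the trial. It does not rescue the figures, because the Section 3 criterion names IA. The four descriptions have to be reconciled before any power statement can be matched to the decision.

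**Power matters little here.** Section 9.4.1 says that significance testing is not relevant, and the decision is made by inspecting standardized differences against d = 0.5. Power to detect d = 0.5 against zero is not the probability of passing that threshold. This limits the consequence. But Section 3 also asks for a significant improvement, and Section 9.2 itself presents the power as justification, so it should describe the planned trial.

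**Stronger readings that the documents do not support.**

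- A reader might infer from the smaller number of visits that true power is well below the stated values. That treats information as proportional to visit count, and ignores both spacing and between-person variation in change. Steps 4 and 5 show that power for a linear IB change could be equal or higher.
- A reader might conclude that the WCST is the weakest of the three criteria and so limits the whole decision. The trained tasks do have higher stated power (.91 to .97), but Section 9.2 gives none for adherence, so the ranking cannot be checked.
- A reader might say that the plan has no WCST power for week 8 or for IA. That can be said only of the running text, because Table 2, to which Section 9.2 refers, was not available for this review.

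**Conclusion.** The point holds as a mismatch of schedule and parameter. The values .77, .78 and .83 are for a change in IB with a week-4 visit and 62.5% of weeks missing. The planned trial has no week-4 WCST and 75% of weeks missing in every window, and its go criterion is IA. The description of these figures as adequate is therefore not supported for the decision to be made.

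The schedule mismatch rests only on the protocol's own text and counting rule. The size and direction of the effect on power are unknown: the illustrations assume two-sided alpha of .05, a linear change, randomly missing weeks in the original simulation and within-person correlations of .3 to .7, and they apply to IB only. This is not a finding that the trial is underpowered. It should be corrected, but it alters no analysis and does not by itself call for a different sample size.

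**What to change.** 1. Make Section 3, Section 8.1, Table 3 and Section 9.4.1 name the same WCST parameter for the go criterion, with one scoring definition.
2. Rerun the simulation for that parameter with observations fixed at weeks 0, 8, 12 and 16, for n=60 and n=48. State the alpha or decision rule, the variance components and how missing visits are generated.
3. Report the result at each of weeks 8, 12 and 16, since each is a candidate duration. Replace the three figures, the week-4 visit, the 62.5% and the word adequate in Section 9.2 accordingly.

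The cost is one simulation rerun and edits to the sections named. Visits, procedures and enrolment do not change. The new figures may be less or more favourable than those now stated.

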9.3 POPULATIONS FOR ANALYSES

All analyses will be conducted on Intention-to-Treat (ITT) Analysis Dataset (i.e., all participants)

9.4 STATISTICAL ANALYSES

9.4.1 GENERAL APPROACH

[figure not shown]
As this is a pilot study, there is no formal SAP

Since our analyses focus on clinically significant magnitude of effects or achievement of thresholds, significance testing is not relevant

We will use Multilevel Structural Equation Modeling (MLSEM) with three levels to estimate changes in levels of Introspective Accuracy (IA) across trials (level 1) and/or weeks (level 2) within persons (level 3). Figure 1 presents an example three-level model wherein changes in IA for the *Variable Length Memory Test* (VLMT) list learning and *Mobile Electronic Test of Emotion Recognition* (METER) emotion recognition are simultaneously estimated. Given the relatively large number of random effects, we will use Bayesian

estimation rather than maximum likelihood estimation for the analyses⁵³. Although some task or ability domains will not be measured at every trial or every week, specifying trial as Level 1 (e.g., for IA on mobile task) and week as Level 2 (e.g., for WCST) will still enable us to estimate changes in IA for these domains.

Figure 1. Three-Level Multilevel Structural Equation Model

As shown in Figure 1, at Level 1 (trials within weeks), participants' judgments of their performance on a task at trial t on week w will be regressed on their objective performance on that same task at trial t on week w (e.g., participants' judgments of their performance on trial t of the list-learning/METER task at week w will be regressed on their objective performance on trial t of that same list-learning task at week w). In line with the Truth and Bias model framework⁵⁴ participants' judgments of their performance will be centered on the grand-mean for objectively assessed performance, and their scores for objective performance will be centered on the mean for their objective performance that week. This centering strategy renders the intercept for participants' judgments of their performance to be the average trial-to-trial difference between their judgment of their performance and the grand-mean for objective performance at week w (e.g., IB for list learning/METER at week w ; see IB-LL/FE in Figure 1). Moreover, the slope for this regression captures participants' capacity to accurately track the lows and highs of their performance across the trials for that week (e.g., IA for list learning/METER at week w ; see IA-LL/FE in Figure 1). To estimate systematic change in IA across the trials (see, e.g., Change in IA-LL/FE in Figure 1), we will regress participants' judgments of their performance at trial t on week w (which is technically IA given the centering strategy) on trial number (grand-mean centered).

The black dots placed on parameters at Level 1 in Figure 1 indicate the estimation of random effects to permit for the heterogeneity of those Level 1 effects across the weeks in the study for participants. Thus, at Level 2 (weeks within persons), we will estimate week-to-week differences in participants' average

levels of IB across the trials, participants' levels of IA, and participants' average changes in IB across the trials (see, e.g., the circles for IB-LL/FE at week w , IA-L/FE at week w , and Change in IB-LL/FE at week w in Figure 1, respectively). Further, to estimate systematic change in IA across the weeks (see, e.g., Change in IA-LL/FE in Figure 1), we will regress participants' IA at week w on week number (grand-mean centered). Because IA is operationalized as a slope (as opposed to a mean-level difference like IB), we estimate change in IA at Level 2 so that reliable estimates of IA can be obtained each week (e.g., 18 trials contribute to IA for list learning). Although not depicted in Figure 1, we will include additional Truth and Bias models at Level 2 for WCST targets of transfer wherein participants' judgments of their abilities assessed at week w are regressed on their objective performance for that domain at week w (e.g., participants' judgments of how many WCST items they got correct at week w will be regressed on their objective performance on the WCST at week w). We will use the same centering strategy described previously to render the intercepts and slopes from the regressions as indices of IB and IA, respectively.

The black dots placed on parameters at Level 2 in Figure 1 indicate the estimation of random effects to permit for the heterogeneity of those Level 2 effects across participants in the study. Thus, at Level 3 (persons), we will estimate individual differences in participants' average levels of introspective bias across the trials and weeks, participants' average levels of introspective accuracy across the weeks, participants' average changes in introspective bias across the trials and weeks, and participants' average changes in introspective accuracy across the weeks (see, e.g., the circles for Mean IB-LL/FE, Mean IA-LL/FE, Mean Change in IB-LL/FE, and Change in IA-LL/FE in Figure 1, respectively). We will evaluate R61 Aim 1 by inspecting the standardized mean-level differences for Change in IA-LL/FE in Figure 1 at weeks 8, 12, and 16. Similarly, we will evaluate R61 transfer of training by inspecting the standardized mean-level differences for changes in IB and/or IA for the WCST.

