8 STUDY ASSESSMENTS AND PROCEDURES

8.1 EFFICACY ASSESSMENTS

Primary Targets: In addition to adherence, the primary Go/No Go targets of the R61 include both IA on trained (METER, VLMT) and untrained task (WCST). During each VLMT and Meter administration, participants are presented with 3 trials where lists of words or faces are presented. For the VLMT, immediately following each exposure to the list, participants were shown target and recognition foil words one-by-one and asked to indicate whether or not the word appeared on the list. For the METER task, participants are asked to guess the emotion in a picture of a human face from among anger, sadness, happiness, no emotion, or fear. After completion of the task, scoring includes the percentage of correct identifications of target words or faces per trial. In embedded validity tests, after each administration, participants self-reported if they were distracted or interrupted.

The reason that trained tasks are part of our Go/No Go criteria is because lack of improvement on trained tasks would call into question the ability of iTEST to modify IA, and would indicate need for program revisions. IA is calculated as the discrepancy (absolute) between each trial's correct performance from that estimated by the participant, which is nested within sessions and weeks. IA on the VLMT and METER tasks predict functional outcomes and is stable over time without training.

An additional Go/No Go component is transfer of training to an untrained task-based measure of IA, the Meta-Cognitive Wisconsin Card Sorting Test¹³. Wisconsin Card Sorting Task (WCST) (Heaton, Chelune, Talley, Kay & Curtiss, 1993). The WCST is a widely used measure of executive function that requires participants to match a presented card to one of four stimulus cards. There are several ways in which the card could be successfully sorted but participants are not informed of the criterion they should use to match the card. Instead, feedback is given after each sort (i.e. correct or incorrect), and participants must use this information to adjust their responses. After each sort, participants are asked to provide a judgement of correctness which are aggregated across sorts and used as the indicator of IA. IA on this task is also associated with functioning and improvement on this task would support that iTEST leads to

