generalized improvement in IA. This adapted WCST was developed by Koren (2006)¹³ and modified by our group³³. The primary measure is the difference in accuracy judgments in relation to correctness³³. Notably, IA on the WCST is stable over repeat administrations. Further, were performance on the WCST to improve with repeated exposures, IA is disconnected from performance (see above) and models will adjust for performance.

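### Section 9.4.1 does not give a usable analysis of the WCST transfer criterion: read literally, the accuracy slope is not identified and the bias term is not adjusted for the participant's own performance

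*Combined protocol and SAP*

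**What the plan says.** Section 9.4.1 uses a truth-and-bias model. For the mobile tasks, judgments are to be "centered on the grand-mean for objectively assessed performance, and their scores for objective performance will be centered on the mean for their objective performance" in that week. The intercept, read as introspective bias (IB), is described as the "average trial-to-trial difference between their judgment of their performance and the grand-mean for objective performance at week w". The slope is introspective accuracy (IA). The section explains that IA, being a slope, needs many observations in a week: "18 trials contribute to IA for list learning".

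The WCST is added at Level 2. Its example regresses the judged number correct at week w on objective performance at week w, and continues: "We will use the same centering strategy described previously to render the intercepts and slopes from the regressions as indices of IB and IA". Transfer is then judged on standardized change in WCST IB and/or IA. Section 9.2 powers that criterion on change in IB.

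Other sections describe the WCST measure differently. Section 3 and Table 3 in Section 8.2 name a global resolution score. Section 8.1 gives the primary measure as accuracy judgments in relation to correctness, says of data collection "After each sort, participants are asked to provide a judgement of correctness which are aggregated across sorts", and answers the practice-effect worry with "IA is disconnected from performance (see above) and models will adjust for performance".

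**The concern.** Outcome and predictor are centered on different things. The intercept therefore compares a participant's judgment with a group average instead of with that participant's own performance, so IB can move when performance moves.

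For the WCST there is a further difficulty. Centering on the person's week mean works with 18 trials in a week. With one total in the week, the mean is the value itself and nothing is left to regress on.

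Transfer to the WCST is one of three go/no-go criteria. If IA cannot be estimated, the decision falls to IB, which under the literal reading ignores own performance. Lower judged scores alone would then look like progress, whether or not self-assessment had become more accurate.

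**Working it through.** **The plan's own figures.** No stated number is in dispute. The nearest are the WCST power values in Section 9.2: .77 (n = 48, 16 weeks), .78 (n = 60, 12 weeks) and .83 (n = 60, 16 weeks). A simple two-sided 5% pre-post calculation, Φ(0.5√n − 1.96), gives .93 for n = 48 and .97 for n = 60. The alpha is my assumption, and the variance components of the simulation are not given. The WCST figures therefore cannot be reproduced, and I do not call them wrong.

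**Intercept.** Let J be judgment and T objective performance. T minus its person-week mean averages zero within the week, so

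IB(w) = mean J(w) − grand mean T = [mean J(w) − mean T(w)] + [mean T(w) − grand mean T].

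The first bracket is bias against own performance. The second is performance itself. With one fixed grand mean, change in IB equals change in mean judgment.

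A simulation of the mobile-task structure (2000 persons, 16 weeks, 18 trials; unbiased judges with perfect tracking) agrees. Performance gains of 0.25, 0.50 and 1.0 SD gave IB changes of 0.25, 0.50 and 1.02 SD. True bias change was 0.00 and the IA slope stayed at 1.00.

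**WCST slope.** With one value per person-week, T(w) − mean T(w) = 0 for everyone. For 60 persons and 4 visits (Sections 1.3 and 3: baseline, weeks 8, 12 and 16) the predictor variance is 0 and the design matrix [1, x] has rank 1. Each person-week supplies 1 observation for 2 parameters.

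**Possible readings for the WCST.**

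| Reading | IA | IB |
|---|---|---|
| Own-week mean, single grand mean | Not identified | Mean judgment minus a constant |
| Own-week mean, week-specific grand mean | Not identified | Average performance change cancels; ability differences remain |
| Person's mean over visits, week in the model | One overall slope (rank 2); change needs a performance-by-week term (rank 4), not stated | Week effect adjusted for within-person performance |

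**Size, single grand mean.** Assumptions, none from the documents: a 5-point gain in percent correct, ability SD 8 to 10, bias SD 6 to 8. If judgments follow performance one for one, the shift is 5/√(8² + 6²) = 0.50 or 5/√(10² + 8²) = 0.39. If a fraction k of the gain passes into judgments, IB moves 5k points: 5 at k = 1, 1.5 at k = 0.3, 0 at k = 0.

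**Size, week-specific grand mean.** The mean shift cancels, but ability variance stays in the denominator. With ability and bias taken as independent, a true d of 0.50 becomes 0.5 × 6/√(8² + 6²) = 0.30 or 0.5 × 8/√(10² + 8²) = 0.31.

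**Raw difference score.** Judgment minus own performance moves by −5(1 − k) points: 0 at k = 1, −3.5 at k = 0.3, −5 at k = 0. It is free of the performance effect only when tracking is complete, so it also needs performance as a covariate.

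**The case against.** The zero predictor rests on a literal reading. In the mobile-task model, trials are centered on the cluster one level up, the week. The parallel for a Level 2 regression is the person's mean over visits. That makes a slope estimable and, with week in the model, adjusts the IB change for performance, consistent with Section 8.1. A simulation at four visits, n = 60, with a 5-point gain and full tracking gave an unadjusted shift of d = 0.37 to 0.46 and an adjusted one of 0.00 (further assumptions: visit-level performance SD 4, judgment noise SD 2). The description of the intercept can also be read as using a week-specific grand mean, which removes the average shift. The WCST regression is given only as an example, for a part of the model not drawn in the figure.

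This stands as far as it goes, and it rules out some stronger inferences:

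- A reader might infer that no WCST slope can be estimated under any reading. Person-mean centering gives one.
- A reader might infer that a practice effect will produce a false shift near d = 0.5. That needs a single grand mean and close tracking, whereas Section 2.2 reports judgments uncorrelated with performance in this population.
- A reader might infer that the trained-task criterion fails too. It rests on change in the within-week IA slope, which this centering leaves intact; only trained-task IB is affected.

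The objection does not supply a per-visit WCST IA, a specified model for its change, or the global resolution score. At week 8 only two scheduled WCST visits exist.

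**Conclusion.** The point holds for the WCST transfer criterion and should be fixed before analysis. Section 9.4.1 states that there is no formal SAP, so it is the operative specification, and no reading of it delivers the declared WCST endpoint or a WCST IA at each visit.

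The literal reading leaves IA unidentified and IB unadjusted for own performance. The kinder readings repair part of this but rely on choices the text does not make: the centering level, whether the grand mean is week-specific, and the performance-by-week term.

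The algebra and the rank result need no numerical assumptions. The effect sizes do. The 0.4 to 0.5 shift assumes full tracking, and the fall from 0.50 to about 0.30 assumes independent ability and bias; both rest on assumed SDs. They show that the effect can matter against a threshold of 0.5. They do not predict what this trial will see.

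**What to change.** For the WCST, replace the regression of one total on one total with scores computed within each visit from the sort-level judgments already collected. Use global resolution as the declared endpoint and judgment minus own performance as bias. Model change from baseline at weeks 8, 12 and 16, with that visit's objective performance as a covariate, as Section 8.1 promises. The covariate is needed for the bias score too, because the raw difference moves when performance alone changes.

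For the mobile tasks, center judgments on the same person-week objective mean, or add that mean as a Level 2 predictor of IB.

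The cost is a small respecification and a few more model terms, with no new data. Section 9.2 powers WCST IB, so its simulation does not cover global resolution and would need to be rerun if power for that endpoint is to be stated.
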